4.1.6.2 Longitudinal repeated measures analysis for outcomes with multiple measurement per week t

Some efficacy parameters (i.e. parameters from CGM or parameters from 6-point SMBG or daily insulin dose) are measured daily during a visit window.

Within each visit window (including baseline and post-baseline visit windows as outlined in Section 6.3), the average for all available data points will be calculated and this will constitute the baseline or Week t value (as applicable).

Analysis will be performed with a longitudinal repeated measurements model as outlined in Section 4.1.6.1.

4.1.6.3 Longitudinal repeated measures analysis model assumption assessment

The assumptions underlying the longitudinal repeated measures analysis model will be checked, if specified in Section 4.2.3. This section also details the steps to follow in case these assumptions would not be satisfied.

Assessment of Treatment-by-Baseline Interaction:

Treatment-by-baseline interaction will be assessed for the Week 24 estimates. In the model defined in 4.1.6.1 and 4.1.6.2, the interaction will be tested by including the treatment-by-baseline interaction.

The following contrast statements will be used of testing for interaction.

- Contrast coefficients for all weeks but Week 24 will be zero.
- Contrast coefficients at Week 24 are presented in Table 3.

Table 3 Contrast Coefficients for the treatment-by-baseline interaction for week 24 estimates

Treatment by baseline interaction	Contrast Coefficients
Dapa 5mg by baseline value	0.5
Dapa 10mg by baseline value	0.5
Placebo by baseline value	-1

The test for interaction will be performed at the 0.10 level of significance. If significant, the interaction will be assessed as qualitative or quantitative. Assessment of the interaction type will be based on regression lines plotted for each treatment group. The intercepts and slopes for these regression plots will be obtained from the analysis model including the interaction term. The intercepts will be estimated by the least squares means. The abscissa of the plots will range from the minimum baseline value from all subjects included in the analysis to the maximum baseline value.

If the regression lines do not cross, or the crossing is judged not severe (i.e., the crossing occurs near the boundary or beyond the range of baseline values), then the interaction will be considered quantitative and this does not compromise the validity of the treatment comparisons. In this case, the treatment comparisons will be made using the model without the interaction term.

Otherwise, the interaction will be considered qualitative and treatment comparisons will not be presented as a result of the complete model. In this case, the impact of the baseline value on treatment effect will be investigated by summarizing the data in subsets defined by baseline categories.

Assessment of Treatment-by-combination of Stratification Factor Interaction:

Treatment-by-combination of stratification factors interaction for estimates at Week 24 will be assessed using method described in Section 4.2.3.1 on primary analysis within subgroups. In the model defined in 4.1.5.1 and 4.1.5.2, the interactions will be tested by including the treatment-by-combination of stratification factor interaction and appropriate contrast statement for testing the interaction in the week 24 estimates. The tests for interaction will be performed at the 0.10 level of significance.

Outlier Detection:

Specifically, an outlier is defined as an observation with a residual that is more than three times the interquartile range above the 75th percentile or below the 25th percentile. Outliers will be identified based on diagnostics performed for the primary efficacy outcome measure using standardized residuals from the longitudinal repeated measurement model. These diagnostics will be based on the box plot. If outliers are present, then additional sensitivity analyses will be performed with the outliers excluded, in order to assess their impact on the results.

Adjustments for baseline imbalances:

Adjustments for baseline imbalances between treatment groups in the longitudinal repeated measures model may be performed as a sensitivity analysis: baseline characteristics for which a clinically important imbalance exists between the treatments will be identified. If such imbalances exist, an adjustment will be performed by including the corresponding baseline characteristics as additional covariates in the longitudinal repeated measures model. This will allow the assessment of the importance of these imbalances on the treatment group comparisons.

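### SAP 4.1.6.3 uses least squares means as intercepts on an uncentred baseline axis, which moves the plotted crossing of the regression lines by the mean baseline (wrong as written, minor)

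*SAP*

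**What the plan says.** SAP Section 4.1.6.3 tests the treatment-by-baseline interaction at Week 24 with the Table 3 contrast (0.5, 0.5, -1): "The test for interaction will be performed at the 0.10 level of significance". If it is significant, a line is plotted for each arm. Both parameters of each line come from the fit that contains the interaction. On the first of them the SAP states: "The intercepts will be estimated by the least squares means". The horizontal axis is raw baseline, drawn from the lowest to the highest value among the analysed subjects.

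A crossing is discounted if "the crossing occurs near the boundary or beyond the range of baseline values". In that event, or when there is no crossing at all, the SAP's conclusion reads: "then the interaction will be considered quantitative and this does not compromise the validity of the treatment comparisons". The comparisons then come from the model that leaves the interaction out. In the remaining case the SAP rules that "the interaction will be considered qualitative and treatment comparisons will not be presented as a result of the complete model", and the data are summarised by baseline category.

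The section does not say at which baseline value the least squares means are evaluated. Section 4.1.6.1 enters baseline as a continuous covariate and does not mention centring. Section 4.1.6.3 says that the model assumptions are checked where Section 4.2.3 specifies it.

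**The concern.** A line's intercept is its height at covariate value 0. Sections 4.1.5.1, 4.1.6.1 and 4.2.3.1 use least squares means for adjusted mean changes and for the differences between arms, which makes sense only at a typical baseline and not at an HbA1c of 0%. A line that takes this adjusted mean as its intercept and then adds slope times raw baseline is not the fitted line.

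The fitted lines and the lines as written have the same slopes but cross at different places. The location of the crossing is what decides the classification, so the error falls on the quantity the rule depends on. At stake is whether a significant interaction is declared harmless or the overall comparison is withheld.

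**Working it through.** **Inputs.** SAP Section 1.3: 243 subjects per arm, SD 1.1, difference 0.35, two-sided level 0.0262, 90% power. SAP Section 1.2: baseline HbA1c strata spanning 7.5% to 10.5%. SAP Section 4.1.6.3: contrast and 0.10 level. The mean and SD of baseline HbA1c are not in the SAP and are assumed over a range below.

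**The plan's own figure.** A two-sample calculation with these inputs returns 243 per arm (power 0.9004); 243/0.95 gives 256 per arm, and 3 x 256 = 768. The design inputs reproduce. The SAP states no figure for the crossing itself.

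**Where the lines cross.** Let L_i be the LS mean at mean baseline m, b_i the slope, and dL and db the differences from placebo.

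- Fitted line: L_i + b_i(x - m). Crossing at x = m - dL/db.
- Line as written: L_i + b_i x. Crossing at x = -dL/db.

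The second is the first minus m. For example, with m = 9.0 (midpoint of the range), dL = -0.35 and db = -0.5, the fitted lines cross at 9.0 - 0.7 = 8.3, well inside the range; the lines as written cross at -0.7.

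**Range of the shift for HbA1c.** With m between 7.5 and 10.5, a true crossing in 7.5-10.5 is plotted no lower than 7.5 - 10.5 = -3.0 and no higher than 10.5 - 7.5 = 3.0, so never on the plotted axis. Conversely, a plotted crossing in 7.5-10.5 needs a true crossing between 7.5 + 7.5 = 15 and 10.5 + 10.5 = 21.

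**How large an effect would be needed.** The SE of the averaged slope contrast is about 1.1 x sqrt(1.5/243)/SD_baseline, and significance at 0.10 needs |db| of at least 1.645 SE. For the averaged line to cross at 7.5 or beyond as written, |dL| must be at least 7.5 x |db|.

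| Assumed baseline SD | SE | smallest significant abs(db) | abs(dL) needed |
|---|---|---|---|
| 0.5 | 0.173 | 0.284 | 2.13 |
| 0.7 | 0.123 | 0.203 | 1.52 |
| 0.87 | 0.099 | 0.163 | 1.23 |

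The design effect is 0.35.

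**Simulation.** 2,000 trials per scenario; single-visit ANCOVA with separate slopes; 243 per arm; residual SD 1.1; baseline normal (8.5, SD 0.8) truncated to 7.5-10.5, giving a mean of 8.65; same effect in both dapagliflozin arms. The true crossing is 8.6 - effect/slope difference. The last two columns give the share of significant interactions in which either dapagliflozin line crosses placebo inside the observed range.

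| Effect at 8.6 | Slope difference | True crossing | Share significant | Fitted lines | As written |
|---|---|---|---|---|---|
| 0 | 0 | none | 0.110 | 100% | 0% |
| -0.35 | 0 | none | 0.100 | 82.5% | 0.5% |
| -0.35 | -0.3 | 7.43 | 0.734 | 78.3% | 0% |
| -0.35 | -0.5 | 7.90 | 0.982 | 93.9% | 0% |
| -0.35 | +0.3 | 9.77 | 0.739 | 99.6% | 0.07% |
| 0 | +0.4 | 8.60 | 0.913 | 100% | 0% |
| -0.1 | -0.4 | 8.35 | 0.921 | 99.8% | 0% |
| -1 | -0.3 | 5.27 | 0.719 | 0.2% | 0% |
| -2 | +0.22 | 17.69 | 0.515 | 0% | 33.7% |

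The last row shows the opposite error: an in-range crossing appears where none exists.

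**The case against.** The strongest reply is that the sentence is underspecified rather than wrong. The model has stratum, week and treatment-by-week terms, so no single coefficient is an arm's Week 24 intercept, and an adjusted mean over strata is a natural way to obtain one. Evaluated at baseline 0, or with a centred covariate and axis, it gives correct lines and no shift. This shows that a programmer could get it right. But the SAP states neither condition, and it uses the term elsewhere for adjusted mean changes. The plot would be correct only if something were added to the written rule. Someone looking at the plot might also notice that each line misses its own adjusted mean by slope x mean baseline, but the repair would then be improvised during the analysis.

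Three further objections stand and limit the point:

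- **Applicability.** Section 4.2.3 cites 4.1.6.1, 4.1.6.2 and 4.1.5.1 but not 4.1.6.3. The interaction paragraph itself says without qualification that the assessment will be made, so whether it runs is unclear.
- **Consequence.** A quantitative result only keeps the prespecified primary model. Section 4.2.3.1 separately reports HbA1c by baseline category, with confidence intervals and an interaction p-value on continuous baseline, so a reversal would not be hidden.
- **Simulation.** It counts any in-range crossing by either dose, whereas the SAP exempts crossings near the boundary and leaves severity to judgement. The percentages for fitted lines are therefore not rates of a qualitative verdict. In the row with no effect and no interaction, correct lines would only turn chance findings into withheld comparisons.

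A reader might infer that the rule returns quantitative whatever the data show, that the primary result is compromised, or that the shift is one known figure such as 8.6 points. The documents support none of these: very large effects produce the opposite error, the primary model is untouched, and no mean baseline is given.

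**Conclusion.** Wrong as written, minor. With the usual least squares mean, the plotted crossing is displaced by exactly the mean baseline. For HbA1c that is 7.5 to 10.5 points, enough to put every true crossing within 7.5-10.5% off the axis whatever the mean is. For other endpoints the shift is the endpoint's own mean baseline, or its mean log baseline if analysed as percent change. In the simulations with average effects from 0 to -1, the lines as written crossed in range in at most 0.5% of significant interactions; at an effect of -2 they did so wrongly in about 34%.

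The algebra needs only the reading of the least squares mean as evaluated at the average baseline. The simulated shares rest further on the assumed baseline distribution and a single-visit model. The error matters only if the check is run and the interaction is significant at 0.10. The primary estimate and its p-value under the prespecified model, and the baseline-HbA1c subgroup results, are unaffected.

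**What to change.** In SAP Section 4.1.6.3, replace the sentence on intercepts with wording to this effect:

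> For each treatment group the Week 24 line is LS mean + slope x (baseline - mean baseline), with the LS mean evaluated at the overall mean baseline. Equivalently, the intercept is the LS mean evaluated at baseline = 0. For endpoints analysed as percent change, ln(baseline) is used throughout.

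Judge crossings on those lines. It would also help to state in Section 4.2.3 for which endpoints the check is run. The cost is a sentence or two of SAP text and one line of plotting code, with no effect on data collection, sample size or the primary model.

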4.2.3.1 Primary efficacy analysis

The primary endpoint is the change in HbA1c from baseline to Week 24. The comparison between each dapagliflozin group and placebo are of interest for this study.

The primary endpoint is the change in HbA1c from baseline to Week 24. The primary estimand for the treatment difference at Week 24 if subjects did not discontinue randomized treatment. The primary analysis of the change in HbA1c from baseline to Week 24 will be based on a longitudinal repeated measures analysis using 'direct likelihood' (see Section 4.1.6.1). The analysis will include all available data up to Week 24 or until premature discontinuation of randomized treatment, whichever occurs first. The analysis will be conducted regardless of insulin up-titration.

The model will use subjects in the primary efficacy dataset (i.e., Full Analysis Set) who have a baseline assessment and any post-baseline double-blind treatment period assessment.

For subjects whose post-randomization insulin dose is up-titrated by more than 25% of insulin relative to baseline, measurements obtained after the first instance the 25% up-titration criteria

is met will correspond to rescue and be included in the primary analysis but excluded in one of sensitivity analyses.

Point estimates and 95% confidence intervals for the mean change within each treatment group as well as the difference in mean change between each dapagliflozin treatment group and placebo will be calculated. Student t-statistics corresponding to the Type III sums of squares for the differences in the least squares means between each dapagliflozin group and placebo at Week 24 will be calculated.

To assess the robustness of the primary efficacy analysis for the change in HbA1c from baseline to Week 24, additional sensitivity analyses will be carried out using the following approaches:

- A longitudinal repeated measures analysis, similar to the primary analysis, excluding measurements obtained after the first instance the 25% up-titration criteria is met.
- ANCOVA analysis including subjects in the Full Analysis Set who have a baseline assessment and at least one post-baseline assessment using LOCF methodology for Week 24 (see Section 4.1.5.1).
- ANCOVA analysis including subjects in the Full Analysis Set who have a baseline assessment and a Week 24 assessment (i.e. a “completers” analysis, but without LOCF methodology) (see Section 4.1.5.1).

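### SAP 4.1.6.3 leaves open whether a significant baseline interaction with crossing lines may withhold the primary Week 24 HbA1c comparison; if it may, a uniformly effective drug loses it by chance in roughly 1% to 8% of trials

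*SAP*

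**What the plan says.** Section 4.1.6.3 opens with a condition: "The assumptions underlying the longitudinal repeated measures analysis model will be checked, if specified in Section 4.2.3". Under its treatment-by-baseline heading it then states, with no condition, that this interaction is to be assessed at Week 24, and names the model: "In the model defined in 4.1.6.1 and 4.1.6.2, the interaction will be tested by including the treatment-by-baseline interaction". Section 4.1.6.1 is the model for the primary endpoint; in Section 4.2.3.1, "The primary analysis of the change in HbA1c from baseline to Week 24 will be based on a longitudinal repeated measures analysis" as set out there.

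The decision rule has three steps.

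- Screen: "The test for interaction will be performed at the 0.10 level of significance", using the Table 3 contrast (0.5, 0.5, -1) on the baseline slopes at Week 24.
- Classification: if the screen is positive, one line per treatment group is plotted. The interaction counts as quantitative if the lines do not cross or if "the crossing is judged not severe (i.e., the crossing occurs near the boundary or beyond the range of baseline values").
- Consequence: "Otherwise, the interaction will be considered qualitative and treatment comparisons will not be presented as a result of the complete model". Summaries in baseline categories take their place.

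Section 4.1.1 bases the primary claim on the two pairwise p-values through the Dunnett-Tamhane step-up procedure. It allows secondary testing only if both primary comparisons are significant.

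**The concern.** A treatment effect that varies with baseline does not invalidate the average effect in a randomized comparison, so it is no reason to withhold that average. The rule makes presentation of the main result depend on a pre-test that is positive in 10% of trials with no interaction at all. It then depends on a visual judgement with no numerical limit for what is near the boundary. The lines are drawn by treatment group, so the judgement needs treatment allocation.

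The two statements about scope pull apart. One makes the check depend on Section 4.2.3, which is silent; the other prescribes it for the primary model. A team could defend either course once the plots exist. If the comparison were withheld, the plan names no replacement test, so the step-up procedure would have no primary p-values and the gate to the six secondary endpoints would be undefined.

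**Working it through.** **Is the rule live for the primary endpoint?**

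- For: the unconditional statement in 4.1.6.3, which refers to the 4.1.6.1 model. The outlier paragraph of the same section is also tied to the primary efficacy outcome.
- Against: the opening condition of 4.1.6.3. Section 4.2.3.1 cites 4.1.6.1 but never 4.1.6.3, and says the Week 24 t-statistics will be calculated. Its subgroup text tests continuous baseline HbA1c by treatment with a nominal p-value and no withdrawal rule.

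The document does not resolve this.

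**The plan's own figures (Section 1.3).** With a difference of 0.35, SD 1.1, two-sided 0.0262 and 90% power:

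n = 2 × (2.2235 + 1.2816)² × 1.1² / 0.35² = 2 × 12.286 × 1.21 / 0.1225 ≈ 242.7, so 243 per arm.

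243 / 0.95 = 255.8, so 256 per arm and 768 in total. The step-up critical value at correlation 0.5 is 2.2235, two-sided p = 0.0262. All of this reproduces.

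**Why chance alone can produce a crossing.** The standard error of the Table 3 slope contrast is 1.1 × √(1.5/243) / SD_b = 0.0864 / SD_b, where SD_b is the SD of baseline HbA1c. The SAP does not give SD_b; 0.58 to 0.87 is assumed.

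- SD_b = 0.58: the standard error is 0.149. A contrast just significant at 0.10 is 1.645 × 0.149 = 0.245 per 1% HbA1c. With a 0.35% effect at the mean baseline, the average dapagliflozin line meets placebo 0.35 / 0.245 = 1.43 points from that mean. The strata span 7.5% to 10.5%, 3.0 points in all.
- SD_b = 0.87 (uniform over the range): the standard error is 0.099, the threshold slope 0.163 and the crossing 0.35 / 0.163 = 2.14 points away. That exceeds the half-width of 1.5, so crossings inside the range are rarer.

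**Simulation.** 6,000 trials per scenario; 243 per arm; residual SD 1.1; no missing data; Week 24 ANCOVA standing in for the repeated measures model; uniform effect of 0.35% on both doses; Table 3 contrast at 0.10; then a crossing inside the observed baseline range. The edge zone is the share of the range at each end treated as near the boundary. The screen was positive in 9.4% to 10.1% of these trials.

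Comparison withheld, dapagliflozin-placebo crossings only:

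| Baseline SD | no edge zone | 10% edge zone | 20% edge zone |
|---|---|---|---|
| 0.58 | 7.9% | 5.9% | 4.3% |
| 0.71 | 7.4% | 5.4% | 3.1% |
| 0.87 | 6.1% | 3.7% | 1.4% |

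If a crossing between any two of the three lines counts, the range is 5.7% to 9.3%. Monte Carlo error is at most about 0.4 points.

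**Effect on power (baseline SD 0.58, 10% edge zone).** Both doses reach p < 0.05 in 89.3% of trials. In 4.95% of all trials they do so and the comparison is withheld, leaving 89.3 - 4.95 ≈ 84.3%. If any crossing counts the deduction is 7.27%, leaving about 82.0%. The 89.3% is the chance that both doses succeed; the plan's 90% refers to one comparison at 0.0262.

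**The case against.** The strongest reply is that the rule never takes effect: the section is conditional, 4.2.3.1 does not invoke it, and neither the t-statistics there nor the step-up rule in 4.1.1 carries an interaction exception. That is a fair strict reading, and it rules out saying that the plan will withhold the primary result. It does not remove the unconditional sentence in the same section, so the status stays open.

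Several stronger inferences are tempting and are not supported.

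- Inflated type I error. No replacement test is named, and withholding a result can remove a rejection but not add one. The 5% limit stands.
- Unplanned subset summaries. The section plans them, and Tables 5 and 7 list baseline HbA1c categories.
- Dose-versus-dose crossings as the main case. The text does not exclude them, but the contrast being classified is average dapagliflozin against placebo, and each dose against placebo is the comparison of interest. They belong only in an upper bound.
- Misplaced lines as a further source of loss. The SAP says "The intercepts will be estimated by the least squares means". Taken literally on the raw baseline axis, this moves crossings far below the baseline range, and simulated withholding falls to about 0%. The percentages above require lines drawn through the least squares means at the mean baseline. The two criticisms cannot apply to the same implementation.
- An untestable interaction. The text names only treatment-by-baseline, but zero coefficients for the other weeks presuppose week-specific terms. The wording is incomplete rather than unworkable.

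**Conclusion.** The concern holds as a conditional one. Section 4.1.6.3 contains a data-dependent rule for withholding treatment comparisons, and the SAP does not settle whether it covers the primary endpoint. If it is applied, a drug with the same 0.35% effect at every baseline value loses its primary comparison by chance in roughly 1% to 8% of trials on dapagliflozin-placebo crossings, and up to about 9% if the two dose lines may also trigger it. The 10% screen caps this chance loss.

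The size depends on the assumed baseline HbA1c distribution (truncated normal or uniform on 7.5% to 10.5%), on the assumed edge zone, on 1.1% as the residual SD, and on correctly drawn lines. What is at stake is power and an interpretable confirmatory result with a defined route to the secondary endpoints. The documents do not show a rule certain to operate, nor a loss of error control.

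**What to change.** Before unblinding:

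- Delete the non-presentation sentence in 4.1.6.3.
- State in 4.2.3.1 that the Week 24 comparisons from the 4.1.6.1 model without the interaction are always presented and always enter the Dunnett-Tamhane procedure.
- Say there whether 4.1.6.3 applies, and keep the baseline interaction as supportive only.
- For that supportive analysis, name the treatment-by-baseline-by-week term and report each dose-minus-placebo difference with its 95% confidence interval across baseline HbA1c. Draw any lines through least squares means at stated baseline values.
- If crossing is still assessed, limit it to dapagliflozin versus placebo and give the edge zone a number.

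The cost is SAP wording; no new data are needed. With the change, the chance of withholding is zero and the probability that both doses succeed stays at about 89% under the assumptions above.
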